12.7. Serious Adverse Events

A SAE is defined as an AE that results in any of the following outcomes:

- Death.
- An immediate threat to life.
- In-patient hospitalization or prolongation of an existing hospitalization subject to the following:
 - Hospitalization is defined as an actual admission, not a 24-hour stay or emergency room visit.
 - Admissions for elective surgeries, undertaken for conditions present prior to receipt of study drug and without complication, should not be considered SAEs.
 - Hospitalization for delivery represents normal obstetrical care and is not an SAE unless precipitated by an unanticipated adverse fetal or maternal event.
- A persistent or significant disability/incapacity (substantial disruption of an ability to conduct normal life functions).
- A congenital anomaly or birth defect.

An important medical event that may not result in death, be life-threatening, or require hospitalization may be considered an SAE when, based upon appropriate medical judgment, it may jeopardize the subject and may require medical or surgical intervention to prevent one of the outcomes listed in this definition. Events which could have led to the above outcomes had they occurred with greater severity are not SAEs, but should be reported as AEs, MAEs, or SNMCs, as appropriate.

A listing of subjects with SAEs will be summarized from Day 0 to Delivery + 180 days for the maternal subjects and from Delivery to Delivery + 180 days for the infants for the unblinded analysis, and from Delivery to Delivery + 364 days for the infants following study completion for the final analysis, for all infants in the Safety Population.

12.8. Vital Signs

Descriptive statistics for vital signs for the maternal subjects (e.g., blood pressure, pulse, respiratory rate, and temperature) on Days 0, 7, 14, Delivery (D), D+35, and D+180 will be presented by treatment group for all maternal subjects in the Safety Population. Temperature

(fever) will be summarized by severity according to regulatory guidance, e.g., Normal $\leq 38.0^{\circ}\text{C}$, Mild = $38.0 - 38.4^{\circ}\text{C}$, Moderate = $38.5 - 38.9^{\circ}\text{C}$, Severe $> 38.9^{\circ}\text{C}$.

Descriptive statistics for vital signs for the infants will be summarized by treatment group based on all the parameters assessed.

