The predominant local reactogenicity profile observed across studies in adjuvanted vaccine recipients included mild to moderate injection site pain/tenderness reported in approximately 70% of all aluminum-adjuvanted vaccine recipients versus approximately 20% of placebo recipients. Swelling, redness, and bruising at the injection site occurred at substantially lower rates by comparison, reported by 10 to 20% of adjuvanted vaccine recipients compared to 1 to 3% of placebo recipients. Injection site reactogenicity did not increase notably in frequency or severity among subjects who received a second dose. Additionally, 10% of subjects may report residual mild injection site discomfort lasting outside the 7-day active solicitation interval.

Systemic reactogenicity reports were generally mild to moderate in severity. The predominant systemic complaints in adjuvanted vaccine and placebo recipients alike were muscle pain (33 and 16%, respectively), headache (36 and 32%), fatigue (30 and 26%); followed by less frequent reports of nausea (17 and 19%), chills (12 and 10%), joint pain (12 versus 7%), diarrhea (12% in both active and placebo), vomiting (3 and 5%), and fever (2 and 1%). Unsolicited adverse event reports of cough, oropharyngeal pain, nasal congestion, upper respiratory tract infection, anemia, nasopharyngitis, pharyngitis, contusion, decreased hemoglobin, rhinorrhea, toothache, rhinitis, viral infection, and pain in extremity were commonly reported (>1 to 10% of subjects) in adjuvanted vaccine recipients. For comparison, all except the nasopharyngitis, rhinitis, contusion, and pain in extremity were also commonly reported in placebo recipients.

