8.8.1 Maternal Subjects

Maternal subjects will be able to indicate severity for any AEs experienced and record this in their diary according to the same scale. For quick reference, an abbreviated grading scale is provided in [Table 6](#) for visible and non-visible local AEs and for systemic AEs for which severity is based on interference with daily activities and not numeric ranges, and in [Table 7](#) for adverse events of nausea, vomiting, diarrhea, fever, and fetal heart tones.

The severity of visually-evaluated local AEs will be a function of size. During the diary period, maternal subjects will monitor the size of visible local AEs at the injection site using the Subject Measurement Tool ([Appendix 4](#)) which has concentric circles that correspond to the diameters

specified in [Table 6](#). For the purposes of reporting during the solicitation period (i.e., Days 0 to 6), the maternal subjects' observations will form the primary data. During clinic visits, investigators may measure any persistent local AEs with a ruler, documenting the size of the reaction at its widest diameter and use the numeric scale provided in [Table 6](#) to assess for severity.

Non-visible local AEs (e.g., pain), solicited systemic AEs (except for those listed in [Table 7](#)), and unsolicited AEs will be assigned a severity based primarily on interference with daily activities ([Table 6](#)). Medical care-seeking is typically absent for grade 1 (mild) and often present for grade 3 (severe) events, but is not the primary determinant, since individuals behave differently in this regard.

Severity of clinical laboratory and vital sign abnormalities (including oral or axillary body temperature, which is captured as a continuous variable) will be graded based on established ranges provided in the TGS, located in **Study Operations Manual**.

Table 6: Severity Grade Definitions for Adverse Events, Maternal Subjects

Severity Grade	Definitions for Local Adverse Events (primarily used for Solicited AEs)		Definitions for Systemic Adverse Events (used for Solicited and Unsolicited AEs)
	Visual Local AE Size Grading Description	Non-Visual Local AE Grading Description	Systemic AE Description (Interference with Daily Activities)
0 – Normal	Reaction size (greatest single diameter) < 2.5 cm	No noticeable symptom	No noticeable symptom or finding

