12.3. Solicited Adverse Events

Solicited AEs for maternal subjects are pre-specified in Section 8.2.1 of the protocol and include both injection site reactions (i.e., pain, bruising, redness, and swelling) and systemic events

(i.e., oral temperature [for assessment of fever], chills, muscle pain, joint pain, diarrhea, nausea, vomiting, headache, and fatigue) that are reported within seven days following the Day 0 vaccination and are solicited by diary. These events are considered related to the study vaccine and are collected using a severity rating of 0 (did not occur), or 1, 2, or 3 (mild, moderate, or severe, respectively), using the maximal severity observed for the specific symptom post-vaccination. Notable exceptions include temperature, which is collected as a continuous variable, and that uses temperature grade ranges established in the toxicity grading scale (TGS), which are applied later in the analysis, and events of injection site redness and swelling, which will be measured using a Subject Measurement Tool (see protocol, [Appendix 4](#)). The Subject Measurement Tool is a transparent acetate sheet imprinted with a set of concentric circles with diameters that correspond to TGS ranges that are also used to assign severity.

Solicited AEs will be tabulated and analyzed by the verbatim terms specified in the diary, and not MedDRA coded. Analysis will use exact diary wording (i.e., “muscle pain” rather than changing it to “myalgia”). Only solicited adverse events which record a start date within the 7-day window of the Day 0 to Day 6 post-vaccination period will be included in the tabular summary and listing of solicited events. Solicited AEs will be presented by treatment group for all maternal subjects.

Solicited AEs, collected from the subject diary, which continue after the collection period (i.e., post-vaccination Day 6) will be captured by verbatim term, on an AE electronic case report form (eCRF) page and flagged in the listing of solicited AEs.

The following summaries of solicited AEs will be presented by treatment group as part of the secondary analysis of safety:

- Summary of solicited treatment-emergent AEs by the verbatim terms specified in the diary and within the post-vaccination window (Days 0 - 6).
- A summary of all solicited AEs by severity (mild, moderate, severe), and within the post-vaccination window (Days 0 - 6).

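### SAP 12.8 places a scheduled-visit maternal temperature of exactly 38.0 °C in both the normal and the mild fever grade, while protocol Table 7 grades it as mild only

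*SAP*

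**What the plan says.** SAP 12.8 (Vital Signs) covers maternal vital signs recorded at visits "on Days 0, 7, 14, Delivery (D), D+35, and D+180 will be presented by treatment group". It adds that temperature "will be summarized by severity according to regulatory guidance, e.g., Normal" and then lists four grades: normal at or below 38.0 °C, mild from 38.0 to 38.4 °C, moderate from 38.5 to 38.9 °C, and severe above 38.9 °C.

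Protocol Table 7 (Section 8.8.1) lists the same four grades with one difference: normal is strictly below 38.0 °C.

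The protocol intends one scale for all maternal temperatures. Section 8.8.1 says that vital-sign abnormalities ("including oral or axillary body temperature, which is captured as a continuous variable) will be graded based on established ranges provided in the TGS"). Section 8.2.4 places the vital-sign grades in the TGS and refers to Table 7 for fever. Section 8.2.1 sends diary temperature to the same two places.

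For the solicited diary events of Days 0 to 6, SAP 12.3 follows that scheme: temperature "uses temperature grade ranges established in the toxicity grading scale (TGS"), applied at the analysis stage. It prints no numeric cut-offs. The TGS itself is in the Study Operations Manual and was not available for this check.

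**The concern.** Grades used to tabulate a continuous measurement must not overlap. Temperature is recorded as a number and graded afterwards, so the programmed boundary decides how a reading on the boundary is counted. In SAP 12.8 two grades share the value 38.0 °C, and nothing in the SAP says which takes precedence.

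The overlap falls at the threshold between fever and no fever, so it affects whether a reading counts as fever at all. The value is also an ordinary one: 100.4 °F converts to exactly 38.0 °C.

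Two programmers could follow SAP 12.8 faithfully and produce different fever counts from the same data, and one of those counts would disagree with the protocol's own scale. SAP 12.8 also cites unnamed regulatory guidance, whereas the protocol says that its vital-sign ranges come from published third-trimester reference values.

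**Working it through.** The documents contain no figure to reproduce here. The check applies both sets of cut-offs to the same readings.

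**Inputs**

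| Grade | SAP 12.8 | Protocol Table 7 |
|---|---|---|
| Normal | ≤ 38.0 °C | < 38.0 °C |
| Mild | 38.0 to 38.4 °C | 38.0 to 38.4 °C |
| Moderate | 38.5 to 38.9 °C | 38.5 to 38.9 °C |
| Severe | > 38.9 °C | > 38.9 °C |

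**Step 1: apply both rules.** Readings are taken to one decimal in °C. From 37.0 to 40.0 there are (40.0 − 37.0)/0.1 + 1 = 31 values. For each value, list every grade whose condition it meets.

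- Protocol Table 7: all 31 values have exactly one grade.
- SAP 12.8: 30 values have exactly one grade, the same as in the protocol. The value 38.0 °C meets both the normal and the mild condition.

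**Step 2: conversion from Fahrenheit.** (100.4 − 32) × 5/9 = 68.4 × 5/9 = 38.0 °C.

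**Step 3: direction of the effect, relative to Table 7.**

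- The program tests normal first: 38.0 °C is graded normal and leaves the fever count.
- The program tests mild first: 38.0 °C is graded mild, as in the protocol, and nothing changes.

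The overlap can lower the count or leave it unchanged. It cannot add a fever.

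**Step 4: which tables are affected.**

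- Scheduled-visit temperature summary: governed by SAP 12.8, so exposed.
- Solicited fever, Days 0 to 6: assigned to the TGS by SAP 12.3, so not exposed unless a programmer borrows the 12.8 cut-offs. They are the only numeric fever grades printed in the SAP, so this could happen, but it would depart from 12.3.
- Vital-sign abnormalities reported as adverse events: protocol 8.2.4 requires at least grade 2, so the boundary between grades 0 and 1 does not change what must be reported.

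**Step 5: after the correction.** With normal set to < 38.0 °C in SAP 12.8, each of the 31 values has one grade and the two documents agree at every value.

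**The case against.** Four things can be said for the SAP.

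First, the cut-offs are introduced as an example of regulatory guidance. That softens their status, but they are still what the section offers a programmer, and they still contradict each other and Table 7.

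Second, the point rests on one symbol, ≤ against <, read from a PDF by a program. That is a fair caution. If the original shows <, the overlap disappears.

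Third, no data are lost. SAP 16.6 puts all recorded eCRF data into listings, so individual readings stay visible. That is true, but the summary table could still be wrong.

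Fourth, and strongest, SAP 12.8 is about scheduled visits. This stands, and it sets the limit of the finding. A reader might infer that solicited fever after vaccination will be under-reported, and might size the loss from the earlier-trial rates in protocol 1.6.2 (2% with adjuvanted vaccine, 1% with placebo), for instance as a share of 0.02 × 3,038 ≈ 61 vaccinated women. The documents do not support that. Those are solicited fever rates, and SAP 12.3 sends solicited fever to the TGS. The documents give no fever rate for the scheduled visits and no share of readings at exactly 38.0 °C in either setting. Nor is a lower count certain, because it depends on the order in which a program tests the grades.

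**Conclusion.** SAP 12.8 is wrong as written, and the error is minor. A scheduled-visit reading of exactly 38.0 °C belongs to two grades in the SAP and to one in the protocol.

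The effect is confined to one value in one descriptive table. Relative to the protocol it can only lower the fever count, and only if the normal grade is tested first. Its size cannot be estimated from the documents. Efficacy, Type I error and power are untouched.

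The conclusion assumes that the ≤ is true to the original PDF and that readings are held to one decimal in °C. It also takes Table 7 as a faithful summary of the TGS, as protocol 8.2.4 presents it.

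**What to change.** In SAP 12.8, print normal as < 38.0 °C and keep mild as 38.0 to 38.4 °C, so that the section agrees with protocol Table 7 and the TGS. Replace the reference to unnamed regulatory guidance with a reference to that scale, so that SAP 12.3 and 12.8 cite the same source. Before editing, check the symbol in the original PDF and confirm that the fever ranges in the TGS match Table 7.

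The cost is one character and one cross-reference. No data collection changes and no protocol amendment is needed. If the vital-sign table has already been programmed, the only further work is to check how 38.0 °C is handled and rerun that table if needed.

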12.9. Laboratory Data

Descriptive statistics (mean, median, standard deviation, minimum and maximum values) for continuous laboratory parameters and/or number (percentage) for categorical laboratory parameters will be presented by treatment group. Change from pre-vaccination (Day 0) to Day 14 post-vaccination will also be presented for all continuous parameters.

All laboratory values will be presented in subject data listings, including any available drug screen parameters, and additional labs ordered by the investigator, if applicable. The following protocol-specified parameters (see protocol, Section 7) will be included in summary tables:

- Hematology
 - White Blood Cell count [w/differential] ($\times 10^9/\text{L}$).
 - Hemoglobin ($\times 10^{12}/\text{L}$).
 - Platelet count ($\times 10^9/\text{L}$).
- Serum Chemistry
 - Serum creatinine ($\mu\text{mol}/\text{L}$).
 - Alkaline phosphatase [ALP] (U/L).
 - Alanine aminotransferase [ALT] (U/L).
 - Aspartate aminotransferase [AST] (U/L).
 - Blood urea nitrogen [BUN] (mmol/L).
 - Total bilirubin ($\mu\text{mol}/\text{L}$).
- HIV, HCB, and HCV antigen tests/serologies as required.

A listing of subjects with laboratory values recorded as newly abnormal following study vaccination and meeting toxicity mild criteria (Grade 2) or above as specified in the TGS for the study, will be presented at Screening and Day 14 for clinical laboratory data. If the number of events warrants, a tabular summary (number and percentage of abnormal laboratory values per TGS criteria) of these data will be included. Tabular summaries by race/ethnicity, nationality or geography, or other demographic features may be created.

Toxicity grade shift summaries by treatment group will be generated for each parameter. A shift table of the change from Screening to Day 14 in toxicity grade rating time-points labeled as “Decrease by 2 grades”, “Decrease by 1 grade”, “Normal” (or “No Change”), “Increase by 1 grade”, “Increase by 2 grades”, etc., will be presented as number (percentage) of total subjects by treatment group. Each of these categories will only be presented when data are available.

Clinical laboratory abnormalities reported as adverse events will be included in the summary of adverse events. These include: 1) laboratory values that show an increase in the toxicity grade relative to baseline values in the same subjects, *and* attain at least Grade 2 (e.g., normal or Grade 1 to Grade 2, or Grade 2 to Grade 3) and 2) clinically significant events the Investigator has classified as an AE. A listing of laboratory values associated with adverse events will be presented, along with all associated laboratory values. AE preferred terms coded to a MedDRA SOC of 'Investigations', will be used to select the AEs in this listing in the data listings. A subset listing will be presented for all Grade 3 laboratory values.

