6.1.1.5 Day 14 (± 2 days) – In-clinic or Home Follow-up Visit

In addition to normal obstetrical follow-up including confirmation of fetal heart tones, all subjects will return to the clinic or will be evaluated by study staff at a home visit on Day 14 for the procedures listed below.

- Vital sign collection (heart rate, blood pressure, respiratory rate, and axillary body temperature).
- Query for any unsolicited AEs, MAEs, SNMCs, and SAEs occurring since the last study visit, and any concomitant medications taken for these events. *A physical exam may also be performed to evaluate any adverse event reported.* Subjects will also be queried regarding symptoms suggestive of RSV infection and, in the event onset is within seven (7) days, will undergo a sampling of upper respiratory secretions for detection of respiratory viruses (see **RSV Illness Surveillance** procedures in Section 6.2).
- Blood draw (10 mL) for post-vaccination clinical safety laboratory assessments (if applicable) and (20 mL) RSV serology. Subjects will be reminded to contact the site to report any severe or serious AE, obstetrical complication, or symptoms suggestive of an RSV infection.
- A replacement Study Identification Card will be offered to all subjects, as needed.
- Schedule the Day 28 visit.

If a subject delivers prior to the Day 14 visit, the procedures discussed above will not be performed and no missed Day 14 visit protocol deviation will be captured. The single exception is the blood draw for the clinical safety laboratory assessment [which only applies to subjects enrolled in the first year of study conduct in any country] that should be obtained at the Delivery visit.

6.1.1.6 Day 28 (± 2 days) – Telephone/SMS Contact, In-clinic or Home Visit Safety Follow-up

Subjects who have not yet delivered will have a safety follow-up performed as a telephone/SMS contact visit using an IRB/IEC-approved script (if applicable), an in-clinic visit, or a home visit. At this visit, whether conducted in-clinic or at home, study staff will assess the general health of the subject and query for any severe unsolicited AEs, SAEs, MAEs, SNMCs, clinical symptoms or signs of a suspected RSV illness, or any new obstetrical complications occurring

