6.1.1.7 Delivery (D) – Hospital Follow-up Visit

Subjects will be counselled to notify the obstetrician of the start of labor and will go to the registered hospital or delivery center for delivery where the following procedures will be performed:

- For applicable subjects (i.e., those enrolled in the first year of study conduct in any country) who deliver prior to the Day 14 visit, collection of a venous blood sample (10 mL) for the clinical safety laboratory assessment.
- Collection of a venous blood sample (20 mL) for RSV serology at any time from admission to the hospital and optimally up to 12 hours post-delivery. Note: In extenuating circumstances such as a delivery on a holiday or weekend, the venous blood sample may be obtained up to 72 hours post-delivery.
- Collection of a cord blood sample (at least 5 mL) by the obstetrician or designee immediately upon delivery. If cord blood is not obtained, then this information should be conveyed to the study staff responsible for the infant, so that infant sera may be collected in lieu of cord blood (see Section 6.1.2, Infant Study Procedures at the Delivery Day visit for details).
- Record vital sign data at admission from the subject's medical chart.
- Query for all unsolicited AEs experienced and concomitant medications taken by, or administered to, the subject since the last clinic visit. (*Note: Routine medications for the management of labor and delivery do not need to be recorded.*)
- Documentation of perinatal management including antibiotic therapy and any medical or surgical interventions for cause.
- Documentation of any GBS screening result and treatment.
- Study staff notification of the infant's primary healthcare provider of the child's anticipated participation in the study before or immediately after delivery.
- Reminder of subjects to contact the site promptly to report any symptoms suggestive of an RSV infection.
- Distribution of a replacement Study Identification Card to all subjects, as needed.

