7.1 Clinical Laboratory Testing

The following laboratory tests will be performed by a qualified central laboratory (unless otherwise stated) designated by Novavax on blood samples collected from maternal subjects enrolled in the first year of study conduct in any country at the screening visit (Days -28 to 0) and on Day 14 (unless the subject delivers prior to this visit at which time the blood sample will be obtained at delivery):

- Serum chemistry – alanine aminotransferase (ALT), aspartate aminotransferase (AST), total bilirubin, alkaline phosphatase (ALP), creatinine, and blood urea nitrogen (BUN).
- Hematology – hemoglobin, platelet count, and white blood cell (WBC) count.

Additional clinical laboratory antigen tests/serologies for HIV, syphilis, HBV, and HCV detection will be performed by a central or local laboratory at the screening visit, if results are not available in prior data collected during the course of the current pregnancy.

A urine pregnancy test will be administered to all maternal subjects at the D+180 visit; a positive result will trigger additional follow-up to determine the outcome of the pregnancy.

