4.3.2. In Maternal Subjects

- Percentages of subjects with solicited injection site and systemic reactogenicity within seven days of vaccination.
- Percentages of subjects with unsolicited (local and systemic) adverse events (AEs), unscheduled medically-attended adverse events (MAEs), significant new medical conditions (SNMCs), and serious adverse events (SAEs) through delivery and six (6) months thereafter.
- Clinical safety laboratory assessments of select serum chemistry and hematology parameters through delivery.

- Percentages of subjects with Caesarean, vaginal, or instrument-assisted vaginal modes of delivery.
- Percentages of subjects with post-immunization onset of specific complications of third-trimester pregnancy and delivery including (but not necessarily limited to):
 - Pregnancy complications:
 - Stillbirth,
 - Preterm birth (moderate to late preterm: 32 to < 37 weeks of gestation; very preterm: 28 to < 32 weeks of gestation),
 - Preterm premature rupture of membranes,
 - Placental abruption,
 - Hypertensive disorders of pregnancy including: gestational hypertension, pre-eclampsia/eclampsia,
 - Third-trimester hemorrhage, and
 - Gestational diabetes.
 - Labor and delivery complications:
 - Emergency Caesarean (C)-section for maternal or fetal indications,
 - Postpartum hemorrhage,
 - Chorioamnionitis, and
 - Maternal fever or infection.

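### SAP 12.9 ties the laboratory change, shift and newly-abnormal outputs to Day 14 and has no place for the delivery sample that replaces Day 14 in women who deliver first

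*SAP*

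**What the plan says.** **Protocol.** Section 7.1 takes safety bloods from women enrolled in the first year of conduct in any country, at screening and on Day 14, "unless the subject delivers prior to this visit at which time the blood sample will be obtained at delivery". Section 6.1.1.7 repeats this for women "who deliver prior to the Day 14 visit, collection of a venous blood sample (10 mL) for the clinical safety laboratory assessment". Section 6.1.1.5 closes the Day 14 visit for a woman who has already delivered, but keeps one item: "The single exception is the blood draw for the clinical safety laboratory assessment". Note 11 to the maternal schedule in Appendix 1 agrees.

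**SAP endpoint.** Section 4.3.2 lists "Clinical safety laboratory assessments of select serum chemistry and hematology parameters through delivery", as does Protocol 3.2.4.2.

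**SAP outputs (Section 12.9).**
- Change table: "Change from pre-vaccination (Day 0) to Day 14 post-vaccination will also be presented for all continuous parameters".
- Shift table: "A shift table of the change from Screening to Day 14 in toxicity grade rating time-points". Its categories "will be presented as number (percentage) of total subjects by treatment group".
- Listing of newly abnormal values at Grade 2 or above, with an optional table: "will be presented at Screening and Day 14 for clinical laboratory data".

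**The concern.** The protocol draws the delivery sample so that a woman who delivers early still has a post-vaccination safety value. The three SAP outputs above are defined by time-points to which that sample does not belong. If they are programmed literally, the sample is collected and then left out of the outputs that describe change since vaccination in each arm.

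The women left out are not a random subset: they are those who delivered soonest after the injection, and many of them will have delivered preterm. Preterm birth and pre-eclampsia are both events of special interest in this trial. The pre-eclampsia definition uses platelet count, serum creatinine and liver function, and the safety panel measures platelets, creatinine, ALT, AST and bilirubin. The three outputs would describe only women still pregnant at the Day 14 visit, although the endpoint runs through delivery.

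**Working it through.** There is no planned figure to reproduce. The check is mainly a comparison of texts, with some arithmetic on who is affected.

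**1. Does any other SAP rule place the delivery sample?**
- SAP 16.6 defines collection windows, including windows at delivery, but for serology samples only.
- SAP 12.8 names delivery as a time-point for maternal vital signs. SAP 12.9, the next section, does not name it for laboratory data.
- Protocol 10.6 asks for shift and change-from-baseline summaries without limiting them to Day 14.
- SAP 17 refers back to the protocol and gives no reason for the narrower choice.

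No rule was found.

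**2. Which laboratory outputs are not tied to Day 14?**
- SAP 12.1: laboratory values summarised by arm for all maternal subjects in the Safety Population.
- SAP 12.2: counts and proportions of laboratory abnormalities by severity.
- SAP 12.9: the opening descriptive statistics, the listing of all values, the adverse event summary, the listing linked to adverse events, and the Grade 3 listing.
- Protocol 8.2.3: a rise in grade from baseline that reaches at least Grade 2 is reported as an adverse event.

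The gap is therefore confined to three outputs. What could be lost from any comparison of arms is mainly mean change and shifts below Grade 2.

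**3. Who is left out?** Vaccination is allowed from 28 weeks to 36 weeks 0 days.
- Vaccinated at the latest date and delivered on Day 13: 36 × 7 + 13 = 265 days = 37 weeks 6 days, which is term.
- Latest vaccination for which a Day 13 delivery is preterm (258 days or fewer): 258 − 13 = 245 days = 35 weeks 0 days.

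So every woman vaccinated at 35 weeks 0 days or earlier who delivers by Day 13 delivers preterm. Those vaccinated later may deliver at term. The visit window is ±2 days, so a woman seen on Day 12 who delivers on Day 13 is unaffected, and one whose visit was set for Day 16 could be affected by a delivery on Day 14 or 15.

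**4. How many?** The documents do not say. The only related planning figure is the loss from about 4,600 women to 4,218 per-protocol infants:
- overall 4,600 − 4,218 = 382, and 382 / 4,600 = 8.3%;
- vaccine 3,038 − 2,786 = 252, and 252 / 3,038 = 8.3%;
- placebo 1,562 − 1,432 = 130, and 130 / 1,562 = 8.3%.

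This counts infants excluded for any reason over all seasons. It gives a rough scale only. A working range of just above 0% to about 8% of women with scheduled safety samples is an assumption.

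**5. Dilution in the shift table.** If a share q of the women counted has no post-vaccination value but stays in the denominator, each reported percentage is (1 − q) times the percentage among women with a value. At q = 0.083 the factor is 1 − 0.083 = 0.917. If q is the same in both arms, the ratio between arms does not change. The SAP does not say which total is meant.

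**The case against.** The strongest reply is that exclusion is being inferred from silence. The SAP never says delivery samples are omitted. The protocol treats the delivery draw as a substitute for Day 14, and Appendix 3 budgets a single post-vaccination safety draw, in the Day 14 row. A programmer could reasonably map the substitute to Day 14. That stands as a possible reading, but it is not written down, and it would pool values taken around labour with ordinary Day 14 values without marking them. A rule is needed either way.

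A second reply is that the important signals are caught elsewhere. This largely stands. Reporting a new Grade 2 or higher value as an adverse event is a rule, not a matter of investigator judgement, and the threshold is essentially that of the newly-abnormal listing. It does not recover continuous change or shifts from normal to Grade 1. The listing linked to adverse events picks up only terms coded to the Investigations class.

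A third reply is that a fixed-time table is defensible, because labour may alter laboratory values and the toxicity grades use third-trimester reference ranges. That stands as an argument for showing delivery samples separately. It does not justify leaving them without a place.

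A reader might infer that these women vanish from the maternal laboratory safety summary, or survive only in raw listings and adverse event reports. The documents do not support that: the summaries in SAP 12.1 and 12.2 and the opening descriptive statistics in 12.9 carry no Day 14 limit. A reader might also take 8.3% as an upper bound. It is not a strict one, because it is a whole-trial infant figure and safety bloods come only from first-year-in-country women.

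**Conclusion.** The point holds for three outputs. As SAP 12.9 is written, first-year-in-country women who deliver before the Day 14 visit have no post-vaccination value in the change table, the shift table or the newly-abnormal listing, although the protocol collects one. They may remain in the shift table's denominator. This departs from the SAP's own endpoint and is narrower than Protocol 10.6.

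The number is unknown and probably small, and the outputs are descriptive. No efficacy conclusion is touched, and new Grade 2 or higher values still reach the adverse event tables. The point deserves correction because the omission is selective on early delivery and the samples already exist. It rests on a literal reading of the stated time-points; if the sponsor's programming already maps the delivery sample, the remaining task is to write the rule down and separate those values.

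**What to change.** In SAP 12.9:
- Define the post-vaccination laboratory time-point as the Day 14 sample, or the delivery sample if delivery came before the Day 14 visit.
- Use it in the change, shift and newly-abnormal outputs.
- Show delivery samples as a separate row by arm, with the number of women contributing one.
- Base percentages on women with both a baseline and a post-vaccination value.

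The cost is a few lines of SAP text and one visit-mapping rule in the programs. No new data are needed. The drawback is that delivery values also reflect labour, so the separate row should be read against the placebo arm.
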